9.10 CHEST RADIOGRAPH

All patients eligible to participate in the study will have a single chest radiograph performed prior to their bronchoscopy, as per our local research bronchoscopy guidelines. The radiation dose associated with a single chest radiograph is minimal (0.02mSv, equivalent to 3 days natural

background radiation) and the risk of adverse effects is negligible (risk of inducing a cancer ~1:1,000,000).

9.11 NASOSORPTION

This minimally invasive technique samples nasal (i.e. upper airway) mucosal lining fluid and offers potential benefits over nasal lavage including improved sensitivity through avoidance of significant analyte dilution (inherent with lavage). Nasosorption will be performed on study visits as per Table 1, prior to bronchoscopy and nasal lavage to avoid contamination by the local anaesthetic (bronchoscopy) or saline (nasal lavage) introduced into the nose.

Two strips of Synthetic Absorptive Matrix (SAM) (Leukosorb, Pall Life Sciences, Hampshire, UK) measuring 7mm x 35mm will be placed inside the participant's nostrils for 2 minutes to obtain samples of nasal lining fluid. This is a painless, minimally invasive procedure that will not require any local anaesthetic.

Each piece of SAM will be placed in a single labelled Spin-X Centrifuge Tube with Filter (Sigma-Aldrich Cat no: CLS8161) containing an assay buffer. This will be transported to the lab on ice for initial processing and transferred to -80°C pending analysis for proteins and cytokines by multiplex immunoassay (e.g. using the Meso Scale Device, MSD).

9.12 NASAL LAVAGE

Nasal lavage is performed on study visits as per Table 1 using the following technique:

- With subjects head extended and soft palate closed, up to 10mL of sterile normal saline is instilled into each nostril using a Pasteur pipette.
- Subjects then gently blow their nose into a sterile universal container or sputum pot.
- Lavage fluid is stored on ice, vortexed and aliquoted for storage at -80°C.

Nasal lavage fluid will be analysed to quantify the degree of viral shedding and determine viral load. Nasal lavage samples pre- and post-rhinovirus inoculation will also be tested for all common respiratory viruses by a PCR panel to exclude coincidental infections. Where possible, nasal lavage fluid will also be analysed for proteins and cytokines by multiplex immunoassay.

9.13 NASAL SCRAPE

Up to four nasal scrapes will be performed on study visits as per Table 1 to obtain nasal epithelial cells. All nasal scrapes will be performed after the collection of nasosorption and nasal lavage samples. They will be collected using the following technique:

- A careful examination of the nose is made to identify the nasal mucosa on the inferior turbinate. A plastic nasal curette (Rhinoprobe, Arlington Scientific) is advanced into the nostril until the tip is placed on the surface of the inferior turbinate. Using a gentle scraping motion a tissue sample is collected. This method of sampling is almost painless, and has been extensively employed in adults and infants.
- Nasal scrapes will be placed in labelled sterile scrape tubes with culture media or flow buffer, for culture and flow cytometry respectively.

9.14 BRONCHOSCOPY

Bronchoscopies will be performed on study visits as per Table 1 in the endoscopy suite at St Mary's Hospital, in accordance with British Thoracic Society (BTS) guidelines [26]:

- Subjects will sign a consent form on entering the study and will sign a separate consent form for each bronchoscopy. The procedure will be explained during the assessment stage and subjects will be given written information specifically regarding bronchoscopies in addition to the Participant Information Sheet.
- Subjects will fast for six hours prior to the procedure.
- Resuscitation equipment (for intubation, ECG monitoring and defibrillation) and necessary drugs (salbutamol, theophylline, adrenaline, hydrocortisone) will be available in the bronchoscopy room.
- Premedication will be given including:
 - Nebulised salbutamol 2.5mg prior to bronchoscopy
 - Sedation with midazolam (2-10mg) and/or fentanyl (25-200mcg) as necessary
 - Lignocaine spray (10%) and solutions (1%) for topical anaesthesia. The total dose will not exceed 7mg/kg or 400mg in total.
- Supplemental oxygen at a rate of 2Lmin⁻¹ is given via a nasal cannula and oxygen saturations and heart rate are monitored with a pulse oximeter continuously. Intravenous access will be mandatory in all cases.
- The subject will be monitored during the bronchoscopy by a separate nurse and a second suitably qualified physician will be present to act as an advocate.
- The following samples will be collected in this order:
 1. Bronchosorption using Synthetic Absorptive Matrix (SAM)
 2. Bronchial brushings
 3. Bronchoalveolar lavage (BAL)
 4. Bronchial biopsy

At the second bronchoscopy, sampling should be performed on the contralateral side to the analogous procedures done at the first bronchoscopy.

- All adverse events (pain, bleeding, hypoxia etc) will be recorded.
- Subjects will be observed for 1-2 hours, nil by mouth, after the procedure.
- Transportation will be arranged as subjects should not drive on the day of the procedure.
- All subjects will have a contact telephone number on discharge.

9.14.1 Bronchosorption using Synthetic Absorptive Matrix (SAM)

Bronchosorption (Mucosal Diagnostics, Hunt Developments Ltd, Midhurst, UK) is a technique to sample bronchial mucosal lining fluid. The main benefit of this technique is the measurement of previously undetectable mediators through avoidance of the significant analyte dilution associated with bronchoalveolar lavage.

- The bronchosorption device is passed down the operating port of the bronchoscope. The distal end of the inner probe incorporates a folded strip of Leukosorb (Pall Life Sciences, Hampshire, UK) measuring 1.8mm x 30mm which are placed on either the right, or left (chosen at random) lower lobe bronchial mucosa for 30 seconds.
- Following sampling, the bronchosorption device is withdrawn back into its sheath and the complete device is removed from the bronchoscope.
- The sampling end of the probe is cut off and treated in an identical way to the nasosorption strips of Leukosorb.

Proteins and cytokines will be measured in the samples (e.g. IL-4, IL-5 and IL-13 by multiplex immunoassay such as MesoScale Discovery (MSD) Th1/Th2 7-plex).

9.14.2 Bronchial brushings

Up to six bronchial brushings will be taken from the lower or middle lobe sub-segmental bronchi with a standard disposable cytology brush at each bronchoscopy:

- Deploy each brush at segmental or sub-segmental carina. Advance 1-2cm but keep the brush in sight. Gently brush the side-wall avoiding any bleeding. If a brush has blood on

it, dispose and flush the bronchoscopic channel with a small volume (2-5ml of sterile saline before proceeding with additional brushes.

- Place each brush in a 2ml screw cap tube containing 1mL RNase-free PBS on ice. Cut the wire and close the cap over the brush.
- Store brushing tubes on ice until further processing.

Cells are removed from the brushes and split into samples to be either cultured for *ex vivo* studies, or used for RNA extraction and analysis.

9.14.3 Bronchoalveolar lavage (BAL)

- The bronchoscope is gently inserted into one segmental bronchus of either the right or left middle lobes.
- BAL is performed by instillation of sterile physiological (0.9%) saline at room temperature in 30ml aliquots to a total of 180-240ml, aiming for a return of ~100ml.
- The BAL fluid is collected into a plastic chamber and transferred to polypropylene tubes for transport on ice to the laboratory.

Samples will be centrifuged to separate the cells and supernatant. The cells will be subject to mRNA analysis and flow cytometry, to identify and separate the different inflammatory cell phenotypes. The supernatants will be analysed for proteins and cytokines (where they are present in sufficient concentrations).

9.14.4 Bronchial biopsy

Six bronchial biopsies will be taken from the segmental and sub-segmental bronchi of the right lower and middle lobe at each bronchoscopy, using Keymed 2mm biopsy channel cupped and fenestrated biopsy forceps [FB-19C-1 (1111065)]. Four biopsies will be placed in 4% paraformaldehyde for preparation of paraffin blocks. Immunohistochemistry staining will be used to detect different phenotypes of inflammatory cells. The remaining two biopsies will be used for mRNA analysis.

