7.3.2. Secondary Mechanistic Analysis

Soluble Mediators:

A total of 32 mediators in nasal samples (taken at day -21, 0, 2, 3, 4, 5, 7, 10) and bronchoscopic samples (taken at day -8, day 5) will be measured for each subject.

Values of soluble mediators obtained from bronchial samples will be presented using summary statistics per treatment group and visit. An additional table will summarise per treatment group (for each mediator) the difference in values between mediators taken at D-8 and D5. Analysis to investigate any difference in effect of OC459 and placebo for each mediator will be performed using the difference in values via unpaired (two-sample) t-test or Mann-Whitney U tests for non-parametric data.

Values of soluble mediators obtained from nasal samples will be presented using summary statistics per treatment group and visit. An additional table will summarize per treatment group (for each mediator) the difference between D-21 and peak value (the highest value measured between D0 and D10).

Taking the difference between D-21 and peak value, analysis to determine the difference in effect of OC459 and placebo for each mediator will be performed using unpaired (two-sample) t-test or Mann-Whitney U tests for non-parametric data.

Differences will be considered significant at $P < 0.05$ within a hierarchy of the primary outcome, and interpreted more cautiously for secondary efficacy outcomes, (likewise more so for exploratory outcomes). All P values are two-sided.

Leukocyte numbers:

Values of leukocyte numbers obtained from bronchial samples / flow cytometry will be presented using summary statistics per treatment group and visit. An additional table will summarise per treatment group (for each cell type) the difference in values between samples taken at D-8 and D5. Analysis to investigate any difference in effect of OC459 and placebo for each cell type will be performed using the difference in values via unpaired (two-sample) t-test or Mann-Whitney U tests for non-parametric data.

Eosinophil counts:

Values of blood and sputum eosinophilia will be presented using summary statistics per treatment group and visit. Analysis to investigate any difference in effect of OC459 and placebo for blood and sputum eosinophilia will be performed using the difference in values via unpaired (two-sample) t-test or Mann-Whitney U tests for non-parametric data.

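### Biopsy side at the second bronchoscopy follows two rules that cannot both be met, and BAL volume is neither standardised nor adjusted for: a minor comparability problem for the mechanistic endpoints

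*Protocol*

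**What the plan says.** **Side of sampling.** Protocol 9.14 lists four procedures in order: bronchosorption, brushings, BAL and biopsy. It then states: "At the second bronchoscopy, sampling should be performed on the contralateral side to the analogous procedures done at the first bronchoscopy". The subsections treat side as follows.

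- Bronchosorption (9.14.1): "placed on either the right, or left (chosen at random) lower lobe bronchial mucosa for 30 seconds". Side is open.
- Brushings (9.14.2): "taken from the lower or middle lobe sub-segmental bronchi with a standard disposable cytology brush at each bronchoscopy". No side is named.
- BAL (9.14.3): "one segmental bronchus of either the right or left middle lobes". Side is open, but the left-sided site is not an anatomical one.
- Biopsy (9.14.4): "Six bronchial biopsies will be taken from the segmental and sub-segmental bronchi of the right lower and middle lobe at each bronchoscopy". Side is fixed, at both visits.

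**BAL volume.** Saline is instilled "in 30ml aliquots to a total of 180-240ml, aiming for a return of ~100ml". Protocol 9.14.1 recommends bronchosorption for its "avoidance of the significant analyte dilution associated with bronchoalveolar lavage". SAP 7.6 deals with detection limits, transformation and AUC, but not with lavage volume.

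**Analysis.** For bronchial mediators, SAP 7.3.2 compares the arms on "the difference in values between mediators taken at D-8 and D5", and it treats leukocytes from bronchial samples in the same way. SAP 7.4.1 compares the Day -8 to Day 5 change in CRTH2+ and EG2+ cells from biopsies, in cells per mm² of tissue. SAP 6.3.2 also lists these biopsy counts as secondary mechanistic variables.

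**The concern.** The biopsy change score takes one sample at Day -8 and one at Day 5 from the same subject. If some operators follow 9.14 and others 9.14.4, some subjects are compared with the same lung and others with the opposite lung. Neither document says that the side is recorded (the CRF is not among them), so the analyst may be unable to tell which rule was used.

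For BAL, a mediator concentration depends on how much saline the airway solute was mixed into. That amount may differ between a subject's two lavages, yet the values are subtracted as they stand. A left-sided operator must also improvise the site.

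What is at stake is the precision and interpretability of the BAL and biopsy results, which serve the objective of showing how OC459 works. The baseline-versus-infection comparisons of inflammatory cells and markers in Protocol 10.2 are the most exposed, because they have no control arm to cancel a visit effect. SAP 7.4.3 also carries forward any cytokine found to be statistically induced by infection, so a spurious or missed induction could change which correlations are run.

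**Working it through.** The plan gives no figure of its own on this point to reproduce.

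**Step 1. Biopsy rules side by side.** Suppose the first bronchoscopy samples the right lung.

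| Rule followed | Day -8 | Day 5 | Conflict |
|---|---|---|---|
| 9.14 | right | left | breaks 9.14.4 |
| 9.14.4 | right | right | breaks 9.14 |

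If the first bronchoscopy samples the left lung, 9.14.4 is broken at once. No sequence satisfies both. The interval is 5 - (-8) = 13 days. BAL, bronchosorption and brushings leave side open, so the conflict is confined to biopsies.

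**Step 2. BAL volume range.** The limits are 180/30 = 6 and 240/30 = 8 aliquots. The ratio is 240/180 = 1.33, or 180/240 = 0.75 the other way, and ln(240/180) = 0.288. Assume the same airway solute mixes into the whole instilled volume, so that concentration scales as 1/volume. The extreme case, 180 ml at Day -8 and 240 ml at Day 5, would then turn a true 1.5-fold rise into 1.5 × 0.75 = 1.125-fold. This is a bound, not an expectation.

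**Step 3. Effect on the tests.** Inputs:

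- 15 evaluable subjects per arm (Protocol 10.1, SAP 4.4).
- No true effect.
- Concentration proportional to 1/volume.
- SD of the log change assumed at 0.5, 0.8 and 1.2, because the documents give none.
- 20,000 simulated trials per case, with t-tests on log changes. The SAP plans a t-test or Mann-Whitney test on differences in values, so this is an approximation.

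*(a) Volume varies independently over 180, 210 and 240 ml, alike in both arms.* The log volume ratio between two visits has SD 0.166. Combined SD = √(SD² + 0.166²):

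- √(0.25 + 0.0276) = 0.53
- √(0.64 + 0.0276) = 0.82
- √(1.44 + 0.0276) = 1.21

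Between-arm bias is about 0 and the two-sided type I error is 0.047 to 0.053.

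*(b) Extreme visit shift in both arms (180 ml at Day -8, 240 ml at Day 5).* Between-arm bias is still about 0, with type I error about 0.05. The within-arm change is biased by -0.29 log units.

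*(c) Shift in one arm only (240 ml at Day 5 in placebo, 180 ml otherwise).* The treatment contrast is biased by 0.29 log units.

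| Assumed SD of log change | (b) false within-arm significance | (c) between-arm type I error |
|---|---|---|
| 0.5 | 54% | 33% |
| 0.8 | 25% | 16% |
| 1.2 | 14% | 10% |

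Cases (b) and (c) are worst cases within the permitted range. The documents do not describe either as expected.

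**The case against.** The strongest reply is that the planned mechanistic tests compare randomised, blinded arms. Whatever operators do about side or volume they do without knowing treatment, so it cancels on average. That stands, and case (a) bears it out.

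Further points for the plan also carry weight.

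- 9.14.4 may be read as a specific rule that overrides the general one. It would then keep the biopsy region the same at both visits, which is not itself a comparability fault. But 9.14 includes biopsy in its list and states no exception, so the text does not settle this.
- Biopsy counts are per mm² of tissue, so lavage volume cannot touch them.
- Bronchosorption provides bronchial mediators without lavage dilution, and BAL supernatant is to be analysed only where concentrations suffice.
- The SAP gives no unit for BAL leukocytes. If they are expressed as proportions, dilution is irrelevant.

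A reader might infer that the mechanistic change scores are confounded with treatment. One route runs as follows: inflamed airways return less fluid, operators add saline to reach the target, and the less inflamed arm is diluted less, hiding a true effect. Because the trial's hypothesis is that OC459 attenuates deterioration, a difference by arm after randomisation is possible, and blinding would not prevent it. But the protocol states a target return without saying that volume is raised when return is poor, and neither document links inflammation to return. Similarly, neither document shows that biopsies at Day -8 add injury-related cells to the Day 5 count. These are possibilities to check once data are recorded, not findings.

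**Conclusion.** Two defects hold. First, Protocol 9.14 and 9.14.4 contradict each other on biopsy side, so side may differ between subjects in the biopsy change scores. This follows from the text and needs no assumption. Second, the BAL site cannot be applied on the left as worded, and instilled volume may vary by one third with no adjustment, although the protocol itself acknowledges substantial lavage dilution.

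The BAL consequence is modest noise in mediator concentrations and in any cell counts expressed per volume: at most 0.50 to 0.53 in SD over the SDs assumed, if volume varies alike in both arms. Within-subject changes could be biased by up to 0.29 log units if volume shifted systematically between visits. The OC459-placebo contrast is biased only if volume or return differs by arm, so calling it confounded goes beyond the documents. These sizes rest on the 1/volume dilution model and the assumed SDs.

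The primary endpoint is a diary score and is unaffected, as are the bronchosorption, nasal, blood and sputum measures. Severity is minor, limited to secondary and exploratory mechanistic endpoints.

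**What to change.** 1. Reconcile Protocol 9.14 and 9.14.4 so that one biopsy-side rule applies to all subjects. This review does not say which. If left-sided biopsies are allowed, the lobes named in 9.14.4 need wording that fits the left lung.
2. Correct the BAL site wording in 9.14.3 so that it can be applied on both sides.
3. Record in the CRF, at each bronchoscopy, the side sampled for each procedure and the BAL volumes instilled and returned. For bronchoscopies already done, retrieve these from procedure records where they exist.
4. Add to SAP 7.3.2 one sensitivity analysis of BAL measures that accounts for instilled and returned volume. Examples are total recovered amount (concentration × returned volume) or adjustment for the change in instilled volume. Expressing results per recovered volume would not help, because a supernatant concentration already is that. State the unit for BAL leukocytes in the same place.

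The cost is a few sentences, a few CRF fields and one extra analysis. Volumes and sides that were not recorded cannot be reconstructed later.

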9.15 SPUTUM INDUCTION

Sputum induction will be performed on study visits as per Table 1, in accordance with ERS guidelines[27].

- Subjects will be pre-medicated with 200µg salbutamol via metered dose inhaler and large volume spacer and baseline FEV₁ measured after 10 minutes.
- If the subject's FEV₁ is ≥60% of predicted, the following procedure should be used:
 - Administer 3-4.5% hypertonic saline via nebulizer.
 - Perform 2-5 minutes of inhalation then stop inhalation and check FEV₁ reading.
 - Repeat this process 3 times (i.e. a maximum of 20 minutes).
- If the subjects FEV₁ <60% of predicted, the following should be used:
 - Use normal saline (0.9%) initially.
 - Perform 30 seconds of inhalation then stop inhalation and check FEV₁ reading.
 - Repeat this process for 1 min and then 2 mins of inhalation.
 - Repeat this process with 3% saline with inhalations of 30 secs, 1 min and 2 mins.
 - Repeat this process with 3-4.5% hypertonic saline for 30 secs, 1, 2, 4, and 8 mins.
- In either case if the subject's FEV₁ drops by 20% at any time, or if the subject experiences excessive coughing, bronchoconstriction, hyperventilation, dyspnoea, dizziness, nausea and vomiting, or an increased wheeze, the induction should be stopped immediately and rescue therapy given.

Sputum plugs are selected from saliva by macroscopic inspection of the sample. An aliquot is analysed, unprocessed, for virus load by quantitative PCR. The remaining sample is processed

and centrifuged to separate the cells, which are then stained and counted for differential cell counts.

9.16 VIRUS INOCULATION

Details of the production and testing of the rhinovirus serotype 16 (RV-16) inoculum have been previously published [28]. This inoculum was prepared under the supervision of the Director of the Medical Research Council Common Cold Unit and was fully safety tested for adventitious agents according to published safety guidelines. It has been stored in individual unopened aliquots in the applicants -80°C freezer since production. It has been used in previous studies at high dose [9, 28-30] and low dose [31] over a time span >15 years. There have been no serious adverse events in any of these studies.

Subjects will be inoculated on a single occasion with stored inoculum, described above, divided equally between the two nostrils. A total dose of 100 TCID₅₀ (tissue culture infective dose; the amount of a pathogenic agent that will produce pathological change in 50% of cell cultures inoculated) is used. This is done slowly with sufficient interval between each spray to ensure maximum contact time between the spray and the nasal and pharyngeal mucosa. Subjects will be asked not to swallow during the procedure to ensure maximal pharyngeal contact. Subjects will also be asked to sniff at each actuation to encourage delivery of particles of inoculum to the lower airway. Identical methods have been used in our previous studies in COPD and asthmatic subjects.

9.17 LOSS TO FOLLOW-UP

Participants who are lost to follow up will not be replaced if they were evaluable (i.e. confirmed rhinovirus infection) and there is sufficient data to assess the primary outcome (i.e. complete diary card of symptoms to day 14 post-rhinovirus infection). Subjects who are lost to follow up and do not meet these criteria will be replaced until a sufficient number of evaluable subjects are reached (n=20).

9.18 TRIAL CLOSURE

The trial will be considered complete when the last patient recruited completes the final visit.

10 STATISTICS AND DATA ANALYSIS

10.1 SAMPLE SIZE CALCULATION

The sample size determination is based on the following assumptions:

Type I error probability $\alpha = 5\%$

Effect size = $(\mu_1 - \mu_0)/\sigma$, where

μ_i = mean PEP in group i ($i=1$: OC459, $i=0$: placebo),

σ = standard deviation of PEP, and

PEP is primary end-point (=total daily lower respiratory symptom scores over d0 to d14).

Based on a previously completed trial with similar design conducted at the same study site [10], σ is estimated to be 21.15 and the effect size equal to 22.21, yielding $n=15$ evaluable subjects per treatment group at 80% power. This is grossed-up for 80% rhinovirus inoculation success and adjusted for expected drop-outs to yield 22 enrolled patients per treatment group.

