The causes of asthma exacerbations are complex and likely to involve one or more of a number of factors including poor control of underlying disease, allergen exposure and viral infection. Respiratory viral infections appear the dominant individual precipitant as they are detected in the great majority of asthma exacerbations in both children (80-85%) and adults (60-80%) [8]. The most commonly detected viruses are human rhinoviruses (~60-80%), and it has been shown that experimentally infected asthmatics with rhinovirus (RV) precipitates an acute exacerbation [9].

The use of experimental RV infection has enabled the study of the mechanisms of asthma exacerbations. These have shown that RV infection leads to increased levels of inflammatory mediators in asthmatic subjects relative to healthy controls (specifically 'type 2 cytokines' e.g. IL-4, IL-5 and IL-13, as well as IL-33 and Prostaglandin D₂), and that these increases correlate with the severity of respiratory symptoms [10]. New treatments have subsequently been developed to targeting those mediators, e.g. an antibody against IL-5 [11].

Studies *in vitro* have found that the binding of Prostaglandin D₂ (PGD₂) to the CRTH2 receptor on inflammatory cells (e.g. Th2 lymphocytes, type 2 innate lymphoid cells) stimulates them to produce the type 2 cytokines implicated in asthma exacerbations [12, 13]. Thus treatment with a CRTH2 antagonist represents an attractive approach to prevent RV-mediated exacerbations in asthmatic patients.

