9.4 CLINICAL SYMPTOM SCORES (INCLUDING ACQ)

Patients will be required to keep a diary card of both upper and lower respiratory tract symptoms during the study period (see Appendices). The diary cards will be commenced 21 days prior to inoculation (on day -21) to derive a baseline symptom score. Symptom scores will be kept daily for 6 weeks post-inoculation until the convalescent visit. Spirometry measurements and drug compliance will be recorded on the same diary cards.

Upper Respiratory Tract Symptoms

The diary card of upper respiratory tract symptoms will be started 21 days prior to inoculation. A total upper respiratory clinical symptom score will be derived using a scale of 0 to 3 (absent, mild, moderate and severe) for each of the following eight respiratory symptoms: sneezing, headache, malaise, fever/chills, nasal discharge, nasal obstruction, sore throat and cough, according to previously established criteria [23]. Symptoms will be recorded at the same time of day and before any procedures such as bronchoscopy are performed. An example is shown below:

Symptom	Day 1	Day 2	Day 3	Day 4	Day 5	Day 6	Day 7
Sneezing							
Headache							
Malaise							

Fever/chills							
Nasal discharge							
Nasal obstruction							
Sore throat							
Cough							
Total score							

0 = absent, 1 = mild, 2 = moderate, 3 = severe

The maximum clinical severity score on any one day would be 24. Individual symptom scores will be accumulated over the six-day period from the onset of the cold and the recording on the day prior to inoculation subtracted. Thus, for a patient who has a score of zero on day -1 prior to inoculation, the maximum cumulative score for the six days is 144.

Lower Respiratory Tract Symptoms

A diary card of lower respiratory tract symptoms will be completed with a scoring system as outlined below:

Symptom	Day 1	Day 2	Day 3	Day 4	Day 5	Day 6	Day 7
Cough on waking							
Wheeze on waking							
Daytime cough							
Daytime wheeze							
Daytime breathlessness							
Nocturnal cough, wheeze, breathlessness							
Total score							

0 = absent, 1 = mild, 2 = moderate, 3 = severe

An exacerbation of asthma is defined as an increase in the total respiratory score of at least 2 points over baseline on 2 consecutive days.

Asthma Control Questionnaire (ACQ)

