Appendix B. Participant daily diary card record

NAME Please score symptoms in the boxes as shown: 0 = no symptoms 1 = mild 2 = moderate 3 = severe

Date																				
Sneezing																				
Runny nose																				
Blocked or stuffy nose																				
Sore throat or hoarse voice																				
Headache or face pain																				
Generally unwell																				
Chill, fever or shivery																				
Cough																				
Total cold score																				
Cough on waking																				
Wheeze on waking																				
Daytime Cough																				
Daytime Wheeze																				
Daytime chest tightness																				
Daytime breathlessness																				
Nocturnal cough, wheeze, breathlessness																				
Total Chest score																				
Medications (name and dose)																				
1.																				
2.																				
3.																				
Spirometry: Peak Flow am																				
FEV ₁ am																				
Peak Flow pm																				
FEV ₁ pm																				

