6.2. Primary Analysis Variable

- The primary endpoint will consist of the sum of uncorrected lower respiratory symptom scores from day 0 to day 14. Daily scores will be out of 21 (seven symptom questions rated from zero to three) creating a potential maximum total score of 315.

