7.2. Primary Analysis

Uncorrected lower respiratory symptom scores collected from D0 to D14 will be aggregated to create an overall total for each patient. Where patient scores are missing, data will be imputed based upon rules set within Section 7.5. Patients missing $\geq 20\%$ of score data will be excluded from any additional per-protocol analyses.

Data will be presented using summary statistics per treatment group and will include median and interquartile range (IQR). A supplementary plot showing individual measurements for both groups with a box & whisker overlay showing median and IQR will be produced.

Primary analysis to test for difference between the mean aggregated scores of the two treatment groups will be carried out using Mann-Whitney U tests. Differences will be considered significant at $P < 0.05$. All P values are two-sided.

An additional secondary analysis will take place correcting the scores for bronchoscopy-related symptoms. Full methodology will be clarified within Section 7.3.1 below.

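### The sample-size paragraph labels a 22.21-point difference as a standardised effect (it is 1.05) and ties its 80% power to no named test or distribution; separately, Protocol 9.4 lists six items for a primary score that has seven elsewhere.

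*Protocol*

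**What the plan says.** Protocol 10.1 defines effect size as (μ1 − μ0)/σ, where the means and SD are those of the total lower respiratory symptom score over days 0 to 14. Taking its figures from an earlier trial at the same site, it then says that σ "is estimated to be 21.15 and the effect size equal to 22.21", giving 15 "evaluable subjects per treatment group at 80% power". SAP 4.4 repeats the definition and the figures. Neither section names the statistical test or the score distribution behind the calculation.

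SAP 7.2 makes the Mann-Whitney U test the primary analysis, with medians and interquartile ranges as summaries, and adds "All P values are two-sided". Protocol 10.2 leaves the choice between a parametric and a non-parametric comparison open.

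For the score itself, Protocol 9.4 says "A diary card of lower respiratory tract symptoms will be completed with a scoring system as outlined below". The table that follows has six symptoms: cough on waking, wheeze on waking, daytime cough, daytime wheeze, daytime breathlessness, and a combined nocturnal item. The diary card in Protocol Appendix B has those six plus "Daytime chest tightness". SAP 6.2 says "Daily scores will be out of 21 (seven symptom questions rated from zero to three) creating a potential maximum total score of 315", and SAP 4.4 gives the same maximum.

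**The concern.** A reader who meets a null result will go to this paragraph to see what the trial could have detected. Taken literally, it assumes a difference of 22.21 standard deviations, which is not a possible planning value. It also does not show that the trial was sized for a difference of about one full SD, which is a large effect.

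The power figure cannot be checked against the planned analysis, because the test behind it is not named and the test that will be run is rank-based. The score being powered also has two definitions inside the protocol, so someone working from section 9.4 alone would compute a different primary endpoint from the one in the SAP.

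**Working it through.** **Inputs.** Two-sided α = 0.05 (5% in Protocol 10.1 and SAP 4.4; two-sided from SAP 7.2). Power 80%, σ = 21.15 and the figure 22.21 (Protocol 10.1, SAP 4.4). Allocation 1:1 (Protocol 5.1). Planned test Mann-Whitney U (SAP 7.2).

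**1. Reproducing n = 15.** The normal approximation is n per arm = 2(z₀.₉₇₅ + z₀.₈₀)²/d², with (1.960 + 0.842)² = 7.85.

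- If 22.21 is a raw difference, d = 22.21/21.15 = 1.050 and n = 2 × 7.85/1.050² = 14.2, which rounds up to 15. This matches the plan.
- If 22.21 is the standardised effect, as the definition says, n = 2 × 7.85/22.21² = 0.03, which rounds up to 1. This does not match.
- A one-sided test with the raw difference would give 12, so the calculation was two-sided.

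**2. Power at 15 per arm, with d = 1.05.**

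| Test and assumed distribution | Power |
|---|---|
| Normal approximation | 82.0% |
| Two-sample t-test (noncentral t, 28 df) | 79.3% |
| Mann-Whitney, normal scores, exact critical values | 75.5% |
| Mann-Whitney, normal scores, large-sample p-value without continuity correction | 77.0% |
| Mann-Whitney, shifted gamma scores, shape 4 / 2 / 1 | 82% / 86% / 90% |
| Mann-Whitney, gamma scores, placebo mean 60 / 50 / 40 / 35 | 82% / 85% / 91% / 95% |

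The Mann-Whitney rows come from simulation: 100,000 trials for normal scores and 50,000 for skewed scores, all with SD 21.15 and mean difference 22.21, and with continuous scores (no ties). The gamma shapes and placebo means are assumptions, because the documents give none. As a cross-check on the normal rows, the asymptotic efficiency of the Mann-Whitney test relative to the t-test is 3/π = 0.955. That makes 15 per arm worth about 14.3, or roughly 77% power.

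With normal scores, the exact test has 79.2% power at 16 per arm and 82.1% at 17.

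**3. Range of the score.** Days 0 to 14 are 15 daily scores.

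- Six items: 6 × 3 = 18 per day, and 18 × 15 = 270.
- Seven items: 7 × 3 = 21 per day, and 21 × 15 = 315.

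**4. Could the item count affect n?** The documents do not say which version of the score gave 21.15 and 22.21. Suppose they came from six items and the trial records seven:

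- if the difference and the SD both grow by 7/6, d stays at 1.05 and n at 15;
- if only the SD grows, d = 22.21/24.675 = 0.90 and n = 20;
- if only the difference grows, d = 25.91/21.15 = 1.23 and n = 11.

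The first case is the neutral one. The other two only bound the uncertainty.

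**The case against.** The strongest reply is that nothing of substance depends on this. The 15 per arm reproduces, 22.21 is plainly a raw difference in the wrong slot, and chest tightness is one row missing from one table. That is fair, and it is why the remedy is wording.

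A reader might infer three stronger things, and the documents support none of them.

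- **That the trial falls short of 80% power.** This holds only if the totals are normal. The score is bounded at zero, and SAP 7.2 plans a rank test with medians, which does not suggest that normality was assumed. For the right-skewed shapes tried above, the same test at 15 per arm exceeds 80%. Those shapes are assumptions, but so is normality. Even with normal scores the gap is 3.0 to 4.5 points.
- **That the protocol scores six items and the SAP seven.** The conflict is inside the protocol: section 9.4 disagrees with Appendix B, to which it refers for the diary, and the SAP agrees with Appendix B. The 45-point gap between the two maxima is not an effect on power.
- **That 22.21 is a contrast of asthmatic with healthy subjects.** Protocol 1.1 cites the same source for the finding that "RV infection leads to increased levels of inflammatory mediators in asthmatic subjects relative to healthy controls". That sentence concerns mediators and does not say which contrast gave 22.21; Protocol 10.1 says only that the earlier trial was of similar design. It is reasonable to ask for the contrast, but its nature cannot be inferred.

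**Conclusion.** Two statements are wrong as written. The effect size contradicts its own definition in both documents: the standardised value is 1.05, not 22.21. The Protocol 9.4 table omits an item of the primary score that the diary card records and the SAP analyses. Neither error changes the stated 15 per arm, provided that the difference and SD apply to the score being collected; the documents do not confirm this.

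The power statement is incomplete rather than shown to be wrong. It matches a comparison of means under normal theory, and it is about 4 points too high for the planned Mann-Whitney test if scores are normal (about 76%). If scores are right-skewed it may be too low. Without a stated distribution, the direction of any discrepancy is unknown.

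**What to change.** In Protocol 10.1 and SAP 4.4, replace the effect-size sentence with wording such as: *mean difference 22.21 points, SD 21.15, standardised effect 1.05; 15 evaluable subjects per arm give about 79% power by two-sample t-test, and about 76% by the planned two-sided Mann-Whitney test if scores are normally distributed.* The last condition must stay in the sentence.

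In both places, also state which version of the score (six or seven items) and which contrast in the cited trial gave 21.15 and 22.21.

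Amend the lower respiratory table in Protocol 9.4 to the seven items of Appendix B and SAP 6.2, with 0 to 21 per day and a maximum of 315.

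The cost is a wording amendment to two documents and a check of the source data. Patient numbers, visits and the planned analysis stay as they are.
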